14.2 Subgroup analysis

The primary endpoint, the completion rate, will be calculated overall and separately for those having Definitive Chemoradiotherapy (dCRT) and Neo-adjuvant Chemoradiotherapy (naCRT).

14.3 Interim Analyses

No formal interim analysis of results is planned for this study.

14.4 Procedures for reporting any deviation(s) from the original statistical plan

Any deviations from the original statistical plan will be described and justified in the final report.

14.5 Final analysis

Final analysis will be after end of study evaluations have been recorded and data has been checked to be complete and accurate. Decision to proceed to a formal phase II will be determined by whether the primary and secondary objectives of this study have been met. If the completion rate is >70% then the trial outcome will be to develop a randomised phase II/ III testing Cytosponge™ in post-CRT follow-up.

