For the Cytosponge™ to have a wider application in oesophageal cancer, including treatment surveillance, a feasibility study is required. One of the important differences from patients with BE is that these patients already have dysphagia which could make swallowing of the capsule or retrieval of Cytosponge™ more difficult. Secondly, radiotherapy would have resulted in inflammation of the surrounding tissue. Sample analysis should be robust enough to differentiate molecular markers of inflammation from that of residual cancer. Finally, although a molecular marker for BE and dysplasia that can be detected by Cytosponge™ is well defined and assessed through immunohistochemistry Trefoil Factor 3 (TFF3) and p53 sequencing, markers for invasive cancer detectable with this device need to be developed and validated.

Benefits

This study will test the acceptability and feasibility of using Cytosponge™ post chemo-radiation. The participants will not benefit directly. However, if this study shows feasibility/acceptability, it will lead to larger studies evaluating its role in surveillance post-dCRT, using the Cytosponge™ at multiple time-points during follow-up. An effective surveillance programme may detect a greater proportion of patients with local-only recurrences treatable by curative salvage resection. It may also lead to a shift in standard care where patients could be offered dCRT as first choice, keeping surgery in reserve for patients who fail dCRT.

Risks

The risk for Cytosponge™ in patients with oesophageal cancer has not been assessed previously. It has however, been tested in >1000 patients with Barrett's esophagus. The most common side-effect is a sore throat. Rare complications could be bleeding, perforation, effects on the airway, the Cytosponge™ getting stuck beyond the tumour or detachment of the Cytosponge™ from the string requiring endoscopy to recover the Cytosponge™.

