3 OBJECTIVES AND ENDPOINTS

Primary Objective	Endpoint
Completion rate	The proportion of consented, evaluable, patients successfully undergoing Cytosponge™ will be presented, with the corresponding 95% confidence interval. The proportion will be calculated overall and separately for those having dCRT and naCRT.
Secondary Objectives	Endpoints
Safety	All serious adverse effects related to the procedure, including bleeding (requiring transfusion) and perforation*
Suitability of sample for biomarker analysis	Quality of material obtained from Cytosponge™ test will be centrally analysed at Cambridge (cellularity, yield and quality of extracted DNA will be used as measure of quality). A positive Cytosponge™ result will be defined as presence of cytological atypia and/or p53 mutation
Acceptance rate	
 1. Proportion of eligible patients approached who consent 2. Proportion of patients who have successfully undergone the procedure & would be prepared to accept the procedure repeatedly if it was to be used for follow-up (data will be captured through questionnaire after procedure)
Tertiary Objectives	Endpoints
Residual disease markers	Level of ctDNA in responders vs non-responders
Cytosponge™ comparative efficacy to biopsy	Level of residual cancer, p53 mutations & other identifiable markers in Cytosponge™, pre & post- treatment biopsies

* A TMG meeting will be called if there are >3 cases of procedure related bleeding requiring a blood transfusion.

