5.3 Evaluations during the study

Evaluations on day 1

On the day the intervention is given:

- Dysphagia score (Mellow Scale)
- Research bloods (optional) if not already collected at Pre-study intervention

Post procedure:

- Assessment of immediate complications (safety monitoring)
- Questionnaire (participants complete post procedure in clinic, or return by post to their recruiting hospital if this cannot be achieved)

Telephone Follow-up evaluations (End of study)

No face-to-face follow-up visit is planned beyond the Cytosponge™ procedure, however patients will have telephone appointments with a qualified member of the research team as per summary of events (week 1 and week 2) to review concomitant medications, dysphagia score and assess for any complications. This can be completed in person if deemed appropriate by the local study team. This is only applicable for participants that have received definitive CRT (not for surgery), or for participants who have received neo-adjuvant CRT, if these times are prior to surgery. This is because the trial is exploring the Cytosponge™ effect on the oesophagus, which will no longer be applicable after this has been removed in surgery.

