## 2. BACKGROUND AND OBJECTIVES

### 2.1 Background and rationale

There are around 8900 new cases of oesophageal cancer in the UK every year and the UK incidence rate is the second highest in Europe for males and the highest for females (CRUK Cancer Statistics, 2013-2015). Surgery is often challenging in oesophageal cancer patients and a non-surgical approach, i.e. definitive chemoradiotherapy (dCRT), may be the preferred treatment, reserving surgery for salvage. Although overall survival in patients treated with dCRT remains comparable to those treated with surgical-based therapy (Stahl et al, 2005), the higher incidence of loco-regional recurrence and the lack of an effective surveillance strategy have deterred many clinicians from adopting dCRT plus salvage surgery as the standard approach. Regular endoscopic surveillance is invasive; this study will investigate the feasibility of a less invasive technique, Cytosponge™, in post CRT surveillance in oesophageal cancer. If found to be feasible, it will lead to larger studies evaluating the role of Cytosponge™ in surveillance post-dCRT. An effective surveillance programme may detect a greater proportion of patients with local-only recurrences treatable by curative salvage resection. It may also lead to a shift in standard care where patients could be offered dCRT as first choice, keeping surgery in reserve for patients who fail dCRT.

There are no Investigational Medicinal Products (IMPs) in this trial. The only study-specific interventional procedure is the investigational Cytosponge™ procedure, which will comply with the MHRA Medical Device Directive. The Cytosponge™ is supplied by Cambridge University Hospital, the legal manufacturer of the device. The Cytosponge™ is not CE marked and not authorised for use in the UK. The trial will be conducted under a Notification of No Objection from the MHRA.

Cytosponge™ test kit, is a Class I, single-use, non-sterile, non CE-marked device that consists of an expandable spherical 3cm diameter mesh, encapsulated in a gelatine capsule, which is attached to a cord. The capsule is swallowed and allowed to reach the stomach while remaining attached to the cord, which is held onto by the patient or a qualified member of the trial team. 3-5 minutes after swallowing (once dissolved in the stomach) the spherical mesh can be retrieved by pulling on the cord. Cells are collected by the mesh scraping against the oesophageal mucosa.

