## Final analysis

Final analysis will be after end of study evaluations have been recorded and data has been checked to be complete and accurate. Decision to proceed to a formal phase II will be determined by whether the primary and secondary objectives of this study have been met. If the completion rate is >70% then the trial outcome will be to develop a randomised phase II/ III study testing Cytosponge™ in post-CRT follow-up.

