#### 6.4 Pre-specified Subgroup Analysis

The primary endpoint, the completion rate, will be calculated overall and separately for patients recruited post definitive chemoradiotherapy (dCRT) and those recruited post neo-adjuvant chemoradiotherapy (naCRT). If patients receiving naCRT have their surgery within the two week follow-up period they will not provide follow-up data.

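### Does the >70% go rule leave open which completion rate decides, and for which follow-on population?

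*Protocol*

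**What the plan says.** Protocol 14.5 has two sentences on what follows the study. The first is general: "Decision to proceed to a formal phase II will be determined by whether the primary and secondary objectives of this study have been met". The second carries the number: "If the completion rate is >70% then the trial outcome will be to develop a randomised phase II/ III testing Cytosponge™ in post-CRT follow-up". SAP 3.7, which is headed as a restatement of the protocol, repeats the rule with one word added: "If the completion rate is >70% then the trial outcome will be to develop a randomised phase II/ III study".

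The endpoint table in Protocol 3 (and SAP 2.2) says of the completion rate: "The proportion will be calculated overall and separately for those having dCRT and naCRT". Three rates will therefore be reported.

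The next study is described in two ways. The go rule speaks of follow-up after CRT. Protocol 1.3 says of a successful result that "it will lead to larger studies evaluating its role in surveillance post-dCRT, using the Cytosponge™ at multiple time-points during follow-up", and SAP 2.1 says "it will lead to larger studies evaluating the role of Cytosponge™ in surveillance post-dCRT". Patients in the naCRT group are due for oesophagectomy (Protocol 4.1). Protocol 5.3 gives this as the reason for stopping their telephone follow-up at surgery: the effect of the device on the oesophagus is something "which will no longer be applicable after this has been removed in surgery".

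**The concern.** A go rule should identify the estimate it is applied to. Here three rates are available and the rule says only that the completion rate must exceed 70%. If the next trial is for patients who keep their oesophagus after dCRT, the dCRT rate could be argued to be the relevant one, and the overall rate mixes in patients who go on to surgery. No dCRT share of the 50 is fixed.

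The risk would be a go decision on the overall rate when the dCRT rate is below the line, or the reverse, with the choice between them made after the results are seen. If the true rates in the two groups also differ, the chance of a go on the overall rate would depend on the recruitment mix.

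**Working it through.** **1. The plan's own figure.** Protocol 13.1 and SAP 3.3 give 50 evaluable patients, an expected rate of 70% and an asymptotic 95% interval. The half-width is 1.96 × √(0.70 × 0.30 / 50) = 0.127, which rounds to the stated 13 points. This statement covers all 50 patients and no subgroup.

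**2. Which rate the text points to.**
- SAP 4.2 gives one population for the completion rate: everyone who consented and attempted to swallow the device.
- SAP 6.1.1 defines the primary outcome as one proportion in that population.
- SAP 6.2.1 analyses it as one rate with one 95% interval and no split.
- Protocol 14.2, SAP 3.7 and SAP 6.4 place the dCRT and naCRT rates under subgroup headings.
- The sample size links 70% to all 50 patients only.

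The unqualified term in the go rule therefore means the overall rate. Since 35/50 is exactly 70%, the rule is met at 36/50 (72%) or more.

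**3. How often the overall and dCRT rates would disagree.** Let X_d ~ Bin(n_d, p_d) and X_n ~ Bin(50 − n_d, p_n), independent. Overall go: X_d + X_n ≥ 36. dCRT above the line: X_d / n_d > 0.70. Disagreement is the sum of the two discordant probabilities, from the exact joint distribution. The documents give no group sizes or group rates, so all of these are assumed. With the same true rate in both groups:

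| True rate | n_d = 20 | 25 | 30 | 40 |
|---|---|---|---|---|
| 70% | 28% | 25% | 21% | 14% |
| 75% | 27% | 20% | 19% | 12% |
| 80% | 17% | 10% | 10% | 5% |
| 85% | 6.6% | 2.5% | 2.6% | 0.9% |
| 90% | 1.1% | 0.2% | 0.2% | <0.1% |

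Example: 17/25 dCRT (68%, exact 95% CI 46 to 85%) and 20/25 naCRT (80%) give 37/50 (74%), a go overall with dCRT just under the line. In every cell of the table the true rates are equal. Disagreement is then sampling noise in a subgroup, and the overall rate is the more precise estimate of the common value.

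**4. What a dCRT threshold would cost.** The half-width at 70% is 1.96 × √(0.21 / n): 20.1, 18.0, 16.4 and 14.2 points for 20, 25, 30 and 40 dCRT patients, against 12.7 for all 50.

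**5. If the true rates differ.** The chance of an overall go then depends on the mix. At an assumed 65% dCRT and 75% naCRT it is 51, 45, 39 and 28% for n_d = 20, 25, 30 and 40. At 65% and 70% it is 33, 30, 28 and 23%. Inserting the word overall in the rule would not alter these figures.

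**6. CRT or dCRT in the follow-on.** The documents use the two terms loosely. Protocol 1.1 discusses surveillance of patients selected for dCRT and then calls it post-CRT surveillance. The clinical rationale in the synopsis moves from dCRT to post-CRT surveillance in the same way, and SAP 2.1 uses both terms in one paragraph. By the reasoning in Protocol 5.3, surveillance of the oesophagus applies only to patients who still have one.

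**The case for a change.** The strongest reply is that a natural reading is not a written rule. The endpoint text itself lists three rates, and no sentence puts the word overall into the go rule. If CRT is shorthand for dCRT, the rule is aimed at dCRT patients but decided partly on others. Protocol 1.1 supplies a reason why naCRT completion is informative, since the hope is to offer dCRT to patients who now have surgery, but no passage connects that reason to the rule. One clarifying sentence would be cheap.

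The observation about wording stands. The consequence does not. The remedy usually proposed has three parts: confirm the overall rate as the criterion, show the dCRT rate and its interval beside it, and name the population of the next trial. The first is what the plan already implies. The second is already planned in Protocol 14, Protocol 14.2 and SAP 6.4. The third belongs to the later trial's protocol. The sensitivity to mix when true rates differ is also real, but this remedy leaves it in place, and a dCRT threshold would rest on fewer patients.

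Nor is there evidence that the rule was shaped by results. SAP V1.0 (22Apr2020) is later than its own expected analysis start (16Mar2020), but it only carries over the rule from the protocol version of 20Feb2019, which predates the end of recruitment on 31Jan2020.

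**Conclusion.** No change follows. Read as a whole, the plan applies the >70% rule to the overall completion rate in all evaluable patients. The dCRT rate will be reported, and the general sentence before the rule leaves room to weigh it with the other objectives. An analyst following the plan as written reaches the same estimate, the same interval and the same go decision as one following a clarified version.

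The 14 to 28% disagreement at a true rate of 70% (5 to 17% at 80%, at most 6.6% at 85%) rests on assumed dCRT numbers of 20 to 40 and no true group difference. It describes how a total and its own subgroup can straddle a cut-off by chance; it is not a rate of wrong decisions. The size of any effect of mix cannot be known, because the documents give no group rates. What is left is editorial: the missing word overall in Protocol 14.5 and SAP 3.7, and two terms for one follow-on setting.

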15 TRANSLATIONAL SAMPLE COLLECTION (OPTIONAL)

CYTOFLOC is an excellent opportunity to prospectively collect biopsy and blood samples for translational research. Translational studies would look at a number of key areas which could include (but not restricted to):

- Co-relate Cytosponge™ sample with endoscopic biopsy
- Baseline diagnostic biopsy
- Blood biomarkers of tumour response

Biopsy sample collection

Participants may consent to their surplus biopsy samples being used by the research team. For patients with baseline diagnostic biopsies, and/or undergoing endoscopic re-assessment of tumour response at around the time of Cytosponge™ testing, optional paraffin tissue blocks of tumour samples should be requested from pathology. These should be posted as instructed in the Device & Sample Handling Manual. All samples should be labelled using the labels provided by OCTO.

Below is one example of standard practice biopsy collection:

Sample	Visible tumour	No visible tumour	Comments
Biopsy in formalin	x2	x2 from previous tumour site	Sample to histopathology.

Blood sample collection

An optional blood sample will be taken if agreed by the participant and will be processed and stored using the procedures in the Device & Sample Handling Manual provided in the Investigator Site File. It is recommended that these samples are taken at the same time as any routine bloods if possible so that participants do not have to undergo any additional venepunctures.

16 STUDY COMMITTEES

16.1 Trial Management Group (TMG)

The TMG will oversee the running of the study. Members of the TMG will include the Chief Investigator, Co-Investigators, Trial Manager, Trial Statistician and others as required. The TMG will meet as necessary.

16.2 Data and Safety Monitoring

There is no independent Data and Safety Monitoring Committee (DSMC) established for this study.

16.3 Trial Steering Committee

Study Oversight will be provided by an independent Radiotherapy & Imaging Trial Oversight Committee (RIOC).

17 DATA MANAGEMENT

17.1 Database considerations

Data management will be performed via a web-based, bespoke study database (OpenClinica). OpenClinica is a dedicated and validated clinical study database designed for electronic data capture. <http://www.openclinica.org>.

A guide explaining how to use OpenClinica will be provided to every site. Relevant OCTO staff will have overview of all entered data.

17.2 Electronic Case Report Forms (eCRFs)

It is important that the investigator makes sure that:

- The relevant eCRFs are completed.
- All eCRF data are verifiable in the source documentation and any discrepancies are explained.
- eCRF events are completed in a timely fashion, as close to the visit or event being recorded as possible.
- Data queries are resolved and documented by authorised study staff, giving a reason for the change or correction where appropriate.

The above considerations also apply to patients who are withdrawn early. If a patient is withdrawn from the study, the reason must be noted on the appropriate form.

17.3 Accounting for missing, unused, or spurious data.

Missing data will be chased up and supplemented where possible after consultation with the investigator. The completeness and correctness of the data will be monitored as per the monitoring plan.

18 CLINICAL STUDY REPORT

All clinical data will be presented at the end of the study as data listings. These will be checked to confirm the lists accurately represents the data collected during the course of the study. The study data will then be locked and a final data listing produced. The clinical study report will be based on the final data listings. The locked study data may then be used for analysis and publication.

19 STUDY SITE MANAGEMENT

19.1 Study site responsibilities

The Principal Investigator (the PI or lead clinician for the study site) has overall responsibility for conduct of the study, but may delegate responsibility where appropriate to suitably experienced and trained members of the study site team. All members of the study site team must complete the Staff Contact and Responsibilities Sheet provided prior to undertaking any study duties. The PI must counter sign and date each entry in a timely manner, authorising staff to take on the delegated responsibilities.

19.2 Study site set up and activation

A Principal Investigator should lead the study at each site, providing the local study office with all core documentation and attend the 'Site Initiation Visit' organised between the site and the Trial Office before the site becomes activated (usually carried out as a telephone conference call or personal visit). The Trial Office will call to check that the site has all the required study information/documentation and is ready to recruit. The site will then be notified once they are activated on the OCTO-CYTOFLOC database and able to register.

19.3 Study documentation

The Trial Office will provide an Investigator Site File to each investigational site containing the documents needed to initiate and conduct the study. The Trial Office must review and approve any local changes made to any study documentation including Patient Information and Consent Forms prior to use. Additional documentation generated during the course of the study, including relevant communications must be retained in the site files as necessary to reconstruct the conduct of the study.

20 REGULATORY & ETHICAL CONSIDERATIONS

Declaration of Helsinki: The investigator will ensure that this study is conducted in accordance with the principles of the Declaration of Helsinki.

Guidelines for Good Clinical Practice: The investigator will ensure that this study is conducted in accordance with relevant regulations and with Good Clinical Practice (GCP), and the applicable policies of the sponsoring Institution and host Trusts.

Participants and their clinical teams will not receive any results from their Cytosponge™ samples. This is because at this feasibility stage we are unclear on the material/data that will be obtained from the Cytosponge™ or how reliable this is. Therefore, the Cytosponge™ should not influence clinical care.

20.1 Ethical conduct of the study and ethics approval

The Protocol, Patient Information Sheet, Consent Form and any other information that will be presented to potential study patients (e.g. advertisements or information that supports or supplements the informed consent) will be reviewed and approved by an appropriately constituted, independent Research Ethics Committee (REC). Principal Investigators will be approved by the REC.

20.2 Regulatory Authority approval

Appropriate approvals will be sought to receive a Notification of No Objection from the MHRA to use the device in the Trial. All reporting to the MHRA will follow the Trial Office's Sponsors' Standard Operating Procedures.

20.3 NHS Research Governance

Investigators are responsible for ensuring they obtain confirmation of capability and capacity to conduct the study in accordance with HRA approval, local arrangements and policies. This confirmation will take the form of fully executed contract or written agreement of Statement of Activities and must be sent to the Trial Office.

20.4 Protocol amendments

Amendments are changes made to the research following initial approval. A 'substantial amendment' is an amendment to the terms of the REC application, MHRA approval or to the protocol or any other supporting documentation that is likely to affect to a significant degree:

- The safety or physical or mental integrity of the subjects of the study;
- The scientific value of the study;
- The conduct or management of the study; or
- The quality or safety of the NIMP/intervention used in the study.

Non-substantial amendments are those where the change(s) involve only minor logistical or administrative aspects of the study.

All amendments will be generated and managed according to OCTRU SOPs to ensure compliance with applicable requirements. Written confirmation of the REC, MHRA and HRA approval must be in place prior to implementation by Investigators. The only exceptions are for non-substantial amendments or any amendments that do not require REC

or MHRA review which will be submitted to HRA, and amendments that are necessary to eliminate an immediate hazard to study patients (see below).

It is the Investigator's responsibility to update patients (or their authorised representatives, if applicable) whenever new information (in nature or severity) becomes available that might affect the patient's willingness to continue in the study. The Investigator must ensure this is documented in the patient's medical notes and the patient is re-consented if appropriate.

